3.2 Randomization

Not Applicable. This is not a randomized study.

3.3 Blinding

Not Applicable. This is an open-label study.

3.4 Determination of Sample Size

Approximately 10 to 15 subjects will be enrolled in this study, at least 1 subject who weighs ≥9 to <11 kg, and at least 4 subjects who are less than 4 years of age at Screening, including at least 1 subject who is 2 years of age. The sample size is not based on statistical considerations and is believed to be adequate to characterize the PK of trofinetide in this population.

4. ANALYSIS SETS

Safety Analysis Set

The Safety Analysis Set consists of all enrolled subjects who received at least one dose of study medication. This analysis set will be used for all safety as well as any descriptive efficacy analyses.

Pharmacokinetics (PK) Analysis Set

The PK Analysis Set consists of all subjects in the Safety Analysis Set with at least 1 quantifiable PK concentration.

5. DATA HANDLING CONVENTIONS

All data collected in the study will be listed.

5.1 General Data Reporting Conventions

Continuous variables will be summarized using the following descriptive statistics: number of subjects, mean, standard error (SE), standard deviation (SD), median, minimum, and maximum. Unless specified otherwise, means and medians will be presented to one more decimal place than the raw data, and the SDs and SEs will be presented to two more decimal places than the raw data. In general, the maximum number of decimal places is 4 and values will be truncated to 4 decimal places in situations where there are more than 4 decimal places. Wherever possible data will be decimal aligned.

Height, weight and BMI will be presented with a maximum of one decimal place.

Categorical variables will be summarized by the number of subjects and the percentage of subjects in each category; the number of subjects and the percentage of subjects with missing data will be summarized for demographic and baseline characteristics (if applicable). Categories with zero counts will be displayed as “- -”. Percentages will be presented with one decimal place.

Duration in months will be calculated as ([number of days / 365.25] *12).

Laboratory values that are collected with “<” or “>” signs will generally be analysed as the numerical value without the sign in tables and figures. In listings, these data will be reported as collected with the sign.

For tables, all subjects will be pooled together as a “Total” group for summary.

5.2 Derived Variables

In general, assessment of total scores will be derived within the analysis datasets. In the event that total scores are also collected on the electronic case report form (eCRF), the derived values will be used for all analyses. Both the raw and derived scores will be presented in listings.

5.2.1 Rett Syndrome Clinical Severity Scale (RTT-CSS)

The RTT-CSS is a clinician-completed rating scale that measures the severity of core symptoms of RTT. The CSS consists of 13 items, 3 of which measure historical or static characteristics: age of onset of regression, age of onset of stereotypes, and head growth; 10 of which measure current function at the time of assessment: somatic growth, independent sitting, ambulation, hand use, scoliosis, language, nonverbal communication, respiratory dysfunction, autonomic symptoms, and epilepsy/seizures. All items are scored during a clinical interview and examination by the

Investigator or qualified designee using either a 5- or 6-point Likert scale. The total score ranging from 0 to 58 will be calculated as the sum of scores for all 13 items. Higher total scores indicate greater severity of symptoms. If there are any missing item scores, the total score will be considered missing.

5.2.2 Clinical Global Impression–Improvement (CGI-I)

The CGI-I scale is used by the clinician to rate how much the subject's illness has improved or worsened relative to a baseline state. A 7-point scale is used from 1=very much improved, 2=much improved, 3=minimally improved, 4=no change, 5=minimally worse, 6=much worse, 7=very much worse.

Higher CGI-I scores denote less improvement in the illness.

5.2.3 Clinical Global Impression–Severity (CGI-S)

The CGI-S is a 7-point scale that requires the clinician to rate the severity of the subject's illness at the time of assessment, relative to the clinician's experience with subjects who have the same diagnosis. Considering total clinical experience, a subject is assessed on severity of illness at the time of rating: 1=normal, not at all ill; 2=borderline ill; 3=mildly ill; 4= moderately ill; 5=markedly ill; 6=severely ill; or 7=extremely ill.

Higher CGI-S scores denote more severe illness.

5.2.4 Caregiver Global Impression–Improvement (CaGI-I)

The CaGI-I scale is a variation of the CGI scale used to ask caregivers for a global assessment of the subject's illness. The scale requires the caregiver to rate how much the subject's illness has improved or worsened relative to a baseline state. A 5-point scale is used from 1=much improved, 2=improved, 3=unchanged, 4=worse, 5=much worse.

Higher CaGI-I scores denote less improvement in the illness.

5.2.5 Overall Quality of Life Rating of the Impact of Childhood Neurologic Disability (ICND) Scale

The overall quality of life score rating of the ICND will be evaluated. The numeric score of the child's overall quality of life ranges from 1 ("Poor") to 6 ("Excellent"); lower overall quality of life scores indicate lower quality of life.

5.3 Data Presentation Conventions

- 1 year = 365.25 days. Year is calculated as (days/365.25) and will be rounded to 1 digit after the decimal point (tenths) for presentation purposes.

- 1 month = 30.4375 days. Month is calculated as (days/30.4375) and will be rounded to 1 digit after the decimal point (tenths) for presentation purposes.
- Body mass index (BMI) is calculated as [weight (kg)/height (m)²]

5.4 Study Day

If the date of assessment occurs on or after the first dose date, then study day will be calculated as (date of assessment – date of first dose) + 1. If the date of assessment occurs prior to the first dose date, then study day will be calculated as (date of assessment – date of first dose). There is no study day 0.

5.5 Baseline Definition

Baseline will be defined as the last non-missing assessment, including those from repeated and unscheduled measurements, before the first trofinetide dose is administered.

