The first dose of study drug will be administered after all Baseline assessments are completed, or, if the Investigator judges that it is too late in the day, on the following day. In that case, the second day is still considered part of the Baseline visit.

The day the first dose is taken will be considered Day 1. A triplicate ECG must be performed 2 hours (±15 minutes) after the first dose. Two PK samples will also be collected after the first dose: the first, 2 hours (± 15 minutes) after dosing, as close as possible to the postdose ECG, and the second, at least 1 hour after the first. Study drug must be discontinued in the event that a post-Baseline QTcF (QT interval corrected using Fridericia's correction method) duration of \geq 500 ms or an increase of \geq 60 ms compared to the average QTcF interval at Baseline (before dosing) is observed.

After Treatment Period A (and the 30-day follow-up period, if applicable) is completed by all participants, an interim clinical study report of those data will be written. A final clinical study report will be written after the entire study is completed.

3.1.3 **Treatment Period B (Up to Approximately 21 Months)**

Treatment Period B is designed to assess the safety and exploratory efficacy of long-term treatment with trofinetide. Treatment Period B is similar in design and objectives to the open-label extension studies in girls and women 5 to 20 years of age.

During Treatment Period B, subjects will have assessments completed at 24 weeks and 52 weeks after the Baseline visit and then every 26 weeks (6 months) thereafter until the study concludes or is terminated. Assessments may be completed in the clinic or off-site. Study visits may be done off-site at the discretion of the Principal Investigator and only with the prior approval of the Sponsor or Medical Monitor.

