6.3.4 Electrocardiograms

All ECGs will be complete, standardized recordings appropriate for the age of the subject, whenever possible. ECGs will be completed in triplicate at Visit 1 (Screening), at Visit 2 (Baseline) predose and at 2 hours (±15 minutes) after dosing, and at Visit 6 (Week 12). A single ECG will be completed at Visit 3 (Week 2), and Visit 4 (Week 4), Visit 5 (Week 8),

Study: ACP-2566-009 Clinical Study Protocol Amendment 2

Visit 7 (Week 24), Visit 8 (Week 52), Visit 9 (Week 78), and Visit 10 (Week 104). For visits at which more than one ECG is completed, the average QTcF interval of all legible ECGs will be used to determine the QTcF interval for that visit.

The subject should rest for ≥5 minutes in a supine position before the ECG is obtained. If it is impractical to rest in supine position due to the subject's medical condition, the subject may remain in a partial supine or other position (e.g., upright in wheelchair) for ≥5 minutes before the ECG is obtained and when the ECG is obtained. ECG tracings (paper or electronic) will be reviewed and interpreted by a qualified clinician for prolongation of the QTcF interval and for other cardiac irregularities. ECG tracings and results (ventricular rate, PR interval of ECG, QRS interval of ECG, QT, QTcF, and QTcB intervals) will be included in the subject's study records.

ECGs will also be read by a qualified central reader. The central reading will be the reading that is entered in the database. The results from the reports from the central reader will also be reviewed by the Investigator. At Screening and Baseline, the average QTcF interval of all legible ECGs will be used to determine eligibility.

If the average QTcF value from the set of ECGs done at Screening is prolonged due to an identifiable cause, and it is medically appropriate to address that cause, a repeat set of triplicate ECGs may be performed during the Screening period and before the Baseline visit with the agreement of the Medical Monitor. In this case, the repeat ECGs will be used in determination of subject eligibility.

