5.6 Analysis Visit Windows

Efficacy, safety, and PK assessments will be summarized by analysis visit as presented in Table 2 below.

Table 2 Analysis Visit Windows

Analysis Visit	Study Visit	Target Study Day	Study Day Interval
Baseline (Day 1)	2	1	≤ 1
Week 2	3	15	2 – 21
Week 4	4	29	22 – 42
Week 8	5	57	43 – 70
Week 12	6	85	71 – 126
Week 24	7	169	127 – 266
Week 52	8	365	267 – 455
Week 78	9	547	456 – 637
Week 104	10	729	638 – 759

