5.6.2 Multiple Measurements within Visit Windows

In the event that more than one assessment falls within a given window, the assessment closest to the target study day will be selected for the by-visit analysis. If two assessments are equidistant from the target study day, then the chronologically last assessment will be used. Exceptions are

made for incomplete assessments, in which case, more complete assessments will be given priority.

For safety analyses where the extreme values should be selected (e.g., overall post-Baseline minimum, overall post-Baseline maximum, and potentially clinically important values), all non-missing post-Baseline values should be considered, regardless of whether the value is selected for the by-visit summaries. All assessments will be presented in data listings.

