15.4 Vital Signs

Vital signs and weight will be collected throughout the study; height will be measured at Screening, Week 12, and Week 104/EOT/ET. Observed vital signs including weight and BMI and the changes from Baseline at each post-Baseline visit will be summarized using descriptive statistics.

Vital sign values will be considered PCI if they meet the criteria listed in [Table 6](#). The number and percentage of subjects with post-Baseline vital signs that are PCI will be summarized at each post-Baseline visit and for overall post-Baseline. For the overall post-Baseline summaries, all post-Baseline values will be considered, including unscheduled and out of window values. Subjects with multiple PCI values for a given parameter will be counted only once for that parameter. For the by-visit summary, the numerator for the percentage is the number of subjects with a post-Baseline PCI vital sign for the given parameter and visit, and the denominator is the number of subjects with non-missing values for the given parameter and visit. For the overall post-Baseline summary, the numerator for the percentage is the number of subjects with at least 1 post-Baseline PCI vital sign for the given parameter, and the denominator is the number of subjects with non-missing Baseline and at least 1 post-Baseline vital sign for the given parameter. A listing of subjects with any PCI vital sign values will be provided.

Table 6 Criteria for Potentially Clinically Important Vital Signs

Vital Sign Parameter	Unit	Criteria			
		Observed Value	And/Or	Change Relative to Baseline	Change from Supine to Standing
Systolic blood pressure (supine or sitting)	mmHg	≥140	And	Increase of ≥20	-
		≤70	And	Decrease of ≥20	-
Diastolic blood pressure (supine or sitting)	mmHg	≥90	And	Increase of ≥15	-
		≤50	And	Decrease of ≥15	-
Pulse (supine or sitting)	bpm	≥131	And	Increase of ≥15	-
		≤50	And	Decrease of ≥15	-
Weight	kg	Not Applicable		Increase of ≥7%	-
				Decrease of ≥7%	-

15.5 **Electrocardiogram (ECG)**

ECGs are collected throughout the study at every visit. Observed values of ECG variables (e.g., heart rate, PR interval, QRS interval, QT interval, and QTc interval) and the changes from Baseline at each assessment time point will be summarized.

QTcB and QTcF will also be categorized into the following categories (msec), and the number and percentage of subjects in each category will be summarized at each visit and for the overall post-Baseline maximum:

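### The SAP omits the protocol's rule of averaging replicate ECGs for QTcF, and its visit windows place the Day 1 two-hour postdose ECG in the Baseline row

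*SAP*

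**What the plan says.** **Protocol.** Triplicate ECGs are taken at Screening, at Baseline before and 2 h after the first dose, and at Week 12. Every other ECG visit has a single tracing (Table S-1 footnote f; 6.3.4). Section 3.1.2 makes the postdose set mandatory: "A triplicate ECG must be performed 2 hours (±15 minutes) after the first dose". Where a visit has more than one ECG, "the average QTcF interval of all legible ECGs will be used to determine the QTcF interval for that visit" (6.3.4, repeated in 4.4.1 and 6.3.4.1). Change is judged against the average predose QTcF.

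**SAP.** The appendix repeats the triplicate schedule, but the analysis rules never mention averaging:

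- 5.5: "Baseline will be defined as the last non-missing assessment, including those from repeated and unscheduled measurements, before the first trofinetide dose is administered".
- 5.6.2, several assessments in one window: the one closest to the target day is taken, and "If two assessments are equidistant from the target study day, then the chronologically last assessment will be used".
- 5.6.2, extremes: "all non-missing post-Baseline values should be considered, regardless of whether the value is selected for the by-visit summaries".
- 5.4: the date of first dose is study day 1, with no distinction between before and after dosing.
- 5.6, Table 2: study day 1 and earlier is Baseline (target day 1); Week 2 starts at day 2.
- 15.5: observed ECG values and "the changes from Baseline at each assessment time point will be summarized".
- 20: no changes from the protocol's analyses are declared.

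**The concern.** PCI changes in safety assessments are part of the primary safety endpoint, and QTcF is one of them. If the SAP is programmed as written, its QTcF values at triplicate occasions are not those the protocol uses. Only Baseline, Day 1 postdose and Week 12 have replicates, but the Baseline value is subtracted in every change score, so a noisier Baseline carries through the whole table.

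The windowing problem is separate. The 2 h ECG is the only one with a stated time after a dose, and it sits near the stated Tmax of about 2 h (Protocol 1.3.1.3). A reader of the by-visit tables would look there for an acute change in QTcF and would find no row for it.

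**Working it through.** The plan states no figure on this point, so there is none to reproduce.

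**Step 1. Where the Day 1 ECGs fall.** For an assessment on the date of first dose, SAP 5.4 gives study day 0 + 1 = 1. The only Table 2 row containing day 1 is Baseline. Two cases follow under 5.6.2:

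- Predose set on the same date: both sets have study day 1, at distance 0 from target. The tie goes to the later one, the postdose set.
- Predose set on the previous date (allowed by Protocol 3.1.2 when it is too late in the day to dose): study day -1, distance |-1 - 1| = 2. The postdose set, at distance 0, is closer and is chosen.

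Either way the Baseline row would show a postdose value, while 5.5 takes the Baseline used for change scores from before the dose. The postdose occasions are Day 1 at 2 h and Weeks 2, 4, 8, 12, 24, 52, 78 and 104. That makes nine, of which one has no post-Baseline row.

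**Step 2. SD of the change in QTcF.** The documents give no SDs. I assume a replicate SD sr of 5, 8 or 12 ms, a visit-to-visit SD sv of 8 or 10 ms, and no drug effect.

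- Last tracing minus last tracing: √(2sv² + 2sr²)
- Week 12 mean of three minus Baseline mean of three: √(2sv² + 2sr²/3)
- Single ECG minus Baseline mean of three: √(2sv² + 4sr²/3)

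At the lowest values (sr = 5, sv = 8) these are √178 = 13.3, √144.7 = 12.0 and √161.3 = 12.7 ms. At the highest (sr = 12, sv = 10) they are √488 = 22.1, √296 = 17.2 and √392 = 19.8 ms. So the SD of the Week 12 change is 13.3-22.1 ms unaveraged against 12.0-17.2 ms averaged. At the seven single-ECG visits, where only Baseline can be averaged, it is 13.3-22.1 against 12.7-19.8 ms.

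**Step 3. Maximum change over the study.** I simulated 400,000 subjects per setting, each with a predose triplicate and nine postdose occasions of 3, 1, 1, 1, 3, 1, 1, 1, 1 tracings. Day 1 predose and postdose share one visit effect. The literal rule subtracts the last predose tracing from the maximum over all tracings. The averaged rule uses occasion means throughout.

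| Maximum change | Literal | Averaged |
|---|---|---|
| >30 ms, range over settings | 7.4-38.5% | 5.3-29.0% |
| >30 ms, sr = 8, sv = 10 | 23.7% | 18.3% |
| >60 ms, sr = 8, sv = 10 | 0.39% | 0.13% |
| >60 ms, largest setting | about 2.5% | 0.8% |

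At sr = 8 and sv = 10, the expected number of 15 girls above 30 ms is 15 × 0.237 = 3.6 against 15 × 0.183 = 2.7. Above 60 ms it is 15 × 0.0039 = 0.06 against 15 × 0.0013 = 0.02. If the two Day 1 sets have independent visit effects, the ranges become 8.7-39.8% against 5.6-29.9% for >30 ms, and at most 3.0% against 0.8% for >60 ms.

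**The case against.** On averaging, the SAP is silent rather than contradictory. Section 1 says it is to be read with the protocol, and section 20 declares no departure. A programmer could therefore treat the averaged QTcF as the assessment on which 5.5 and 5.6.2 operate. That reading is open, and it is why I do not say the tables will be wrong. But 5.5 expressly counts repeated measurements, and the extremes rule takes all values, so the unaveraged reading is at least as natural. The SAP should settle which applies. It refers date imputation, laboratory coding and compliance details to separate specifications, but not ECG replicates.

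On the Day 1 ECG, 5.5 could be held to override the tie rule, and the promise in 15.5 of results at each timepoint could be held to cover the 2 h set. Table layouts are in separate documents that I have not seen. Against this, SAP 15 says ECG changes are shown by analysis visit, and Table 2 defines no postdose visit on Day 1.

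Three limits on size stand. The postdose ECG is not lost, because it enters the overall maxima, PCI counts and listings. The effect at the >60 ms PCI limit is well under one girl; the larger differences are in the >30 ms category, which is descriptive. All SDs are assumed, and no hypothesis test depends on the tables.

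**Conclusion.** The concern holds on both parts. Followed literally, the SAP gives QTcF values at Baseline, Day 1 postdose and Week 12 that differ from the protocol's averages, without declaring it. It also puts a postdose ECG in the Baseline row and gives that ECG no post-Baseline by-visit row. Under the assumed SDs the literal rules add about 2 to 11 percentage points to the chance that a girl's maximum change exceeds 30 ms by noise alone. In the middle case (sr = 8, sv = 10) that is nearly one extra girl in 15. At >60 ms the addition is at most about 2 points. Part 2 follows from the stated day and window rules and needs no assumption about variability. This should be corrected, but it does not threaten the study's conclusions.

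**What to change.** Amend SAP 5.5, 5.6.2 and 15.5 as follows:

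- Average all legible replicate ECGs at each timepoint before applying the baseline, window and maximum rules. Define ECG Baseline as the mean of the predose triplicate.
- Restrict the Baseline row to predose ECGs, and add Day 1, 2 h postdose as a separate post-Baseline ECG timepoint.
- Write the QTc categories as continuous intervals (for example >450 to ≤480 and >10 to ≤30 ms), because means can fall between the present integer limits, such as between 30 and 31 ms.

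The data are already collected. The cost is SAP wording and programming, with no added visit or ECG.

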5.6 Analysis Visit Windows

Efficacy, safety, and PK assessments will be summarized by analysis visit as presented in Table 2 below.

Table 2 Analysis Visit Windows

Analysis Visit	Study Visit	Target Study Day	Study Day Interval
Baseline (Day 1)	2	1	≤ 1
Week 2	3	15	2 – 21
Week 4	4	29	22 – 42
Week 8	5	57	43 – 70
Week 12	6	85	71 – 126
Week 24	7	169	127 – 266
Week 52	8	365	267 – 455
Week 78	9	547	456 – 637
Week 104	10	729	638 – 759

5.6.1 Unscheduled Assessments

Both Scheduled and Unscheduled assessments, including the assessments at early termination visits, will be included for planned timepoint analyses based on the above analysis visit windowing rules. All assessments will be presented in data listings.

5.6.2 Multiple Measurements within Visit Windows

In the event that more than one assessment falls within a given window, the assessment closest to the target study day will be selected for the by-visit analysis. If two assessments are equidistant from the target study day, then the chronologically last assessment will be used. Exceptions are

made for incomplete assessments, in which case, more complete assessments will be given priority.

For safety analyses where the extreme values should be selected (e.g., overall post-Baseline minimum, overall post-Baseline maximum, and potentially clinically important values), all non-missing post-Baseline values should be considered, regardless of whether the value is selected for the by-visit summaries. All assessments will be presented in data listings.

5.7 Missing or Incomplete Date for Last Dose of Study Drug

For subjects with completely missing last dose date, the last dose date will be imputed by the last expected dosing date, defined as the earliest of the following three dates:

- the non-missing drug return date of the last dispensed drug kits,
- the last drug dispensed date plus the number of days that the dosing would continue if given to the subject per protocol,
- EOT/ET date.

For subjects with partial missing last dose date, the imputation will be compared against the last expected dosing date as defined above. Detailed imputation algorithms will be documented in a separate programming specifications document. The missing or incomplete dates will be displayed in the data listings as reported on the eCRF rather than the imputed dates.

